### TIBIAL TRAY:

The Triathlon TS Total Knee System is compatible with the Triathlon TS Universal Tibial Baseplate, which is intended for use in a cemented application. The root catalog number for the Triathlon TS Universal Tibial Baseplate is:

5521-B-XXX – Triathlon TS Universal Tibial Baseplate

The Triathlon TS Universal Tibial Baseplate, or tibial tray, is available in sizes 1 - 8, is fabricated from cast cobalt-chromium-molybdenum alloy and is neutral in configuration. The undersurface of the tibial tray and keel are grit blasted for interdigitation with PMMA bone cement. The keel of the tibial tray is designed with normalizations for rotational stability and cement interdigitation. The superior aspect of the tibial tray has a rim that contains tabs that mate with the outer periphery of the tibial insert, along with the locking wire used on the tibial insert. This locking feature is designed to provide secure attachment of the tibial insert to the tray, and is designed to reduce micromotion of the tibial insert on the tray.

### **TIBIAL INSERTS**

A total stabilizing tibial insert has been developed for use with the Triathlon TS Total Knee System, in sequentially cross-linked UHMWPE (X3) and N2Vac. The Triathlon TS Plus Tibial Insert is available in sizes 1 - 8, with thicknesses ranging from 9 mm to 31 mm. Each insert size is provided in nine thicknesses to vary the resection gap.

#### CONFIDENTIAL

The tibial insert design is intended to provide  $\pm 2^{\circ}$  of varus/valgus constraint when mated with the Triathlon TS Femoral Components.

The Triathlon TS Plus Tibial Insert features a preassembled cobalt chrome locking wire that secures the tibial insert in the groove of the Triathlon TS Universal Tibial Baseplate. The Triathlon TS Plus Tibial Insert also features a support post that accommodates a cobalt chrome tibial support pin, assembled intraoperatively. The tibial insert support pin is intended to provide additional strength and structural integrity of the knee construct compared to other systems without a support post.

The Triathlon PS Tibial Insert is also compatible with the Triathlon TS Total Knee System and may be used in this study. The root catalog numbers for the tibial inserts permissible according to this study protocol are:

5537-G-XXX – Triathlon TS Plus Tibial Insert 5532-G-XXX – Triathlon PS Tibial Insert, X3 5532-P-XXX – Triathlon PS Tibial Insert, N2Vac

X3 polyethylene is a highly cross-linked polyethylene manufactured through a proprietary process where the polyethylene receives 30 kiloGrays of gamma radiation, which generates free radicals and cross-linking in UHMWPE prior to machining. The polyethylene is then annealed below melting point to promote cross-linking and maintains mechanical strengtha, crystallinityb and densityc. This also stabilizes the free radicalsd. This process is repeated twice.

 $^\circ$  X3 UHMWPE increases cross-link density over N2Vac gamma sterilized UHMWPE by 87%, as measured by swell ratio, per ASTM F2214. Cross-link density, as measured by swell ratio, was 0.08  $\pm$  0.00 mol/dl and 0.15  $\pm$  0.01 mol/dl for N2Vac UHMWPE and X3 UHMWPE, respectively.

#### CONFIDENTIAL

<sup>a X3 UHMWPE maintains mechanical properties for Tensile Yield Strength and Ultimate Tensile Strength of N2Vac gamma sterilized UHMWPE as measured by ASTM D638. Tensile Yield Strength was 23.2  $\pm$  0.4 MPa and 23.5  $\pm$  0.3 MPa for N2Vac UHMWPE and X3 UHMWPE, respectively. Ultimate Tensile Strength was 54.8  $\pm$  2.5 MPa and 56.7  $\pm$  2.1 MPa for N2Vac UHMWPE and X3 UHMWPE, respectively.

<sup>b X3 UHMWPE has similar crystalline and lamellar structure as N2Vac gamma sterilized UHMWPE as measured by Small Angle X-ray Scattering (SAXS) and Differential Scanning Calorimetry (DSC) analysis. DSC determined crystallinity was  $61.3 \pm 0.8\%$  and  $61.7 \pm 0.6\%$  for N2Vac UHMWPE and X3 UHMWPE, respectively. Lamellar crystal thickness was 23.0 and 23.6 nanometers for N2Vac UHMWPE and X3 UHMWPE, respectively.

### PATELLAR COMPONENTS:

Triathlon Patellar Components for use with the Triathlon TS Total Knee System are available in symmetric and asymmetric styles. The components are intended for use in a cemented application for the purposes of this study protocol. The cementless (metal-backed) option in the asymmetric patellar component design is not permissible.

The root catalog numbers for the Triathlon Patellar Components are:

5550-G-XXX – Triathlon Patellar Component, Symmetric, X3 5550-L-XXX – Triathlon Patellar Component, Symmetric, N2Vac 5551-G-XXX – Triathlon Patellar Component, Asymmetric, X3 5551-L-XXX – Triathlon Patellar Component, Asymmetric, N2Vac

The symmetric design is available in six diameters (27 mm, 29 mm, 31 mm, 33 mm, 36 mm and 39 mm) and four thicknesses (8 mm, 9 mm, 10 mm and 11 mm). The symmetric design features a central cement recess and three pegs on the bone interface surface. The Triathlon Symmetric Patellar Component is intended to be implanted via a resurfacing or inset surgical technique. The asymmetric design is available in five superior/inferior dimensions (29 mm, 32 mm, 35 mm, 38 mm and 40 mm) and three thicknesses (9 mm, 10 mm and 11 mm). The asymmetric design features a flare in the lateral aspect of the component. The asymmetric patellar component also has a central recess with three pegs for cement fixation. The Triathlon Asymmetric Patellar Component is intended to be implanted using a resurfacing surgical technique.

### ACCESSORIES:

#### Stems

Fluted stems, manufactured from titanium alloy, are offered in diameters of 10-25 mm (in 1 mm increments) and lengths of 100 mm and 150 mm. The fluted stems are designed to attach to both the femoral and tibial components of the Triathlon TS Total Knee System. One end of the

#### CONFIDENTIAL

<sup>d X3 UHMWPE virtually eliminates free radicals, as measured by Electron Spin Resonance (ESR). A very low (noise level, near instrument detection limit) concentration of residual free radicals was detected in the X3 UHMWPE. A 99% reduction of free radicals ( $14 \pm 2 \times 10^{14}$  spins/gram versus 1550  $\pm$  32 x 10^14 spins/gram) was found when compared to N2Vac gamma sterilized UHMWPE.

fluted stems is threaded and locks into the threaded boss of the femoral and tibial components. The stems are tapered and have a 16 mm diameter at the base, which corresponds to the boss diameter of the Triathlon TS Universal Tibial Baseplate and the Triathlon TS Femoral Component. The stems are intended for use when additional length and stability are required in the tibia or femur. The fluted stems are intended to be implanted without the use of bone cement. The root catalog numbers for the Triathlon Fluted Stems are:

> 5565-S-XXX – Triathlon Fluted Stem, 100 mm 5566-S-XXX – Triathlon Fluted Stem, 150 mm

In the event a cemented stem is needed, the components are offered in diameters of 9 mm, 12 mm and 15 mm, with lengths of 50 mm, 100 mm or 150 mm.

The root catalog number for the Triathlon Cemented Stem is:

5560-S-XXX - Triathlon Cemented Stem

### Stem Extenders and Offset Adapters

Stem extenders and offset adapters will be available for use with the Triathlon TS Total Knee System. The Triathlon Stem Extenders provide additional stem length options for the system (25 mm and 50 mm), while the Triathlon TS Offset Adapters allow for varying stem placement within the femoral and tibial canals.

Each component is manufactured from cobalt chrome and is designed to attach to the Triathlon TS Femoral Component, Triathlon TS Universal Baseplate and stems. Additionally, the stem extenders can be attached to the offset adapters. The Triathlon Stem Extenders and Triathlon TS Offset Adapters have the male thread of the stems and the female thread of the tibial tray and femoral component stem bosses.

The root catalog numbers for the stem extenders and offset adapters permissible for use according to this study protocol are:

5571-S-XXX – Triathlon Stem Extender 5570-S-XXX – Triathlon TS Offset Adapter

#### CONFIDENTIAL

#### Femoral Augments

For cases with severely inadequate medial or lateral femoral bone stock requiring additional fixation of the femoral components, femoral augments are included in this system. Posterior and distal femoral augment components are available for attachment to the Triathlon TS Femoral Component with a locking screw. The Triathlon TS Femoral Components feature a threaded hole that accepts the locking screws.

The femoral distal augments are made from cobalt chrome and are grit-blasted. The augments are offered in sizes 1 - 8 and are available in 5 mm, 10 mm and 15 mm thicknesses with right and left options. The posterior femoral augments are also made from cobalt chrome and are grit-blasted. The posterior augments are provided in sizes 1 - 8 with 5 mm and 10 mm thicknesses. The femoral augments have a threaded hole that accommodates a cobalt chrome locking screw, packaged with the augment. The Triathlon Femoral Augments can be cemented to the Triathlon TS Femoral Component.

The root catalog numbers for the femoral augments and accompanying locking screw permissible according to this study protocol are:

5540-A-XXX – Triathlon Femoral Distal Augment, 5 mm 5541-A-XXX – Triathlon Femoral Distal Augment, 10 mm 5542-A-XXX – Triathlon Femoral Distal Augment, 15 mm

5543-A-XXX – Triathlon Femoral Posterior Augment, 5 mm 5544-A-XXX – Triathlon Femoral Posterior Augment, 10 mm

5540-A-000 – Triathlon Femoral Augment Locking Screw 5545-A-000 – Triathlon Femoral Augment Locking Screw

### Tibial Augments

Medial and lateral tibial augment components are available in right and left configurations for mechanical attachment to the Triathlon TS Universal Tibial Baseplate. The tibial augments are attached to the baseplate and a pre-assembled setscrew is then rotated to engage with a slot machined into the outer edge of the baseplate keel. This allows the tibial augment to lock

#### CONFIDENTIAL

securely onto the baseplate. The tibial augments are made from cobalt chrome and are offered in sizes 1 - 8, in 5 and 10 mm thicknesses.

The root catalog numbers for the tibial augments permissible according to this study protocol are:

5545-A-XXX – Triathlon Tibial Half Block, 5 mm Augment 5546-A-XXX – Triathlon Tibial Half Block, 10 mm Augment

## 6.2 Device Retrieval Process

Stryker Orthopaedics will retrieve any Triathlon TS Total Knee System components and/or adjacent tissues for analysis to help characterize potential device-related complications. In the event that any portion of the Triathlon TS Total Knee System is removed from a study subject, the procedure outlined in the Retrieval Analysis Protocol (Appendix I) should be followed. In addition:

- 1. When revision of a study subject is scheduled, the study coordinator (SC) should contact the Clinical Study Manager (CSM) or Clinical Study Associate (CSA) assigned to the project, as soon as possible.
- 2. The CSM or CSA will send a retrieval container to the SC.
- 3. After the device is explanted, the SC or an identified Stryker field representative will retrieve the device and place it in the retrieval container, following the instructions in Appendix I.
- 4. The SC, an identified field representative or the CSM/CSA will complete a Product Experience Report (PER).
- 5. If not completed by the CSM or CSA, the PER should be faxed to Stryker Product Surveillance at [contact], as well as to Stryker Clinical Research at [contact].
- The PER should be attached to the retrieval container and sent to Product Surveillance.
   A de-identified operative report should be included, when available.
- 7. The CSM or CSA will follow up with Product Surveillance to obtain a PER number.
- 8. A summary of results will be provided to the investigator upon his/her request.

### CONFIDENTIAL

# 7 Evaluations

## 7.1 Preoperative Visit

During the preoperative visit, patients that are possible candidates for this study will be screened to determine if they meet the inclusion/exclusion criteria. If the patient is a candidate, the investigator will propose participation in the study to the patient, according to GCP guidelines. Patients must sign an IRB approved study consent form prior to participating in any study related activities. Consent must be obtained within four months of surgery.

Once the subject has been consented, preoperative data will be collected including: demographics, medical history, KSS, AP, ML and Merchant (30° of flexion) radiographs, SF-36, KOOS, HSS Patella Score, and LEAS. All information collected preoperatively will be used to quantify the sample population and compare postoperative progress.

## 7.2 Surgery

Surgical details will be collected from the operative notes and at the time of surgery. Additional information, other than standard operative notes, includes the following measurements: study-specific surgical times; navigation data, if applicable; flexion-extension gap measurements and component fit. Measurements, in millimeters, of the thickness of the flexion and extension space between the ME and the JL will also be collected.

## 7.3 6-week Visit

During the 6-week visit (± 2 weeks), the following evaluations will be collected: KSS, AP, ML and Merchant (30° of flexion) radiographs.

## 7.4 6-month Interval

During the 6-month interval (± 2 weeks), completion of the following evaluations is required: SF-36, KOOS, HSS Patella Score and LEAS.

## 7.5 Annual Follow-up Visits

Clinical data will be collected via office visit by the investigator at the following annual postoperative intervals: 1-year, 2-year and 5-year. Tools for postoperative evaluation will be the KSS, AP, ML and Merchant (30° of flexion) radiographs.

### CONFIDENTIAL

Patient outcomes data will also be collected via patient questionnaires. At each of the 1-year, 2year and 5-year follow-up visits, the SF-36, KOOS, HSS Patella Score and LEAS are required. Patient questionnaires may be given to subjects in the office during intervals that require clinical data collection.

## 8 Adverse Events

## 8.1 Reporting of Adverse Events

The AE reporting requirements for this study are as follows:

- All AEs that meet the definition of serious, excluding elective procedures
- All AEs related to the operative site, regardless of seriousness

Elective procedures meeting the definition of an SAE do not need to be reported as AEs according to this study protocol. Examples of such elective procedures include, but **are not limited to**, the following commonly seen events:

- Contralateral TKR
- Total Hip Replacement
- Rotator Cuff Surgery
- Cataract Surgery

Such events will not be captured on the AE CRF but rather will be captured on the postoperative functional evaluation at the 6-week, 1-year, 2-year and 5-year time points. On these functional evaluations, investigators and SCs will be prompted to question subjects as to whether they have seen a doctor for any reason, been hospitalized for any reason or have a current impediment to their function.

The following decision tree facilitates identification of AEs for which reporting is required under this study protocol:

### Page 26

### CONFIDENTIAL

### Figure 2. Adverse Event Decision Tree

### **General Physical Examination Findings**

At screening for inclusion into the study, any clinically significant abnormality should be recorded as a preexisting condition and reported on the Demographics CRF. From the time of consent forward, any new clinically significant findings or abnormalities that meet the definition of a protocol defined AE must also be recorded and documented as an AE.

### Adverse Event Reporting Period

The study period during which AEs must be reported is normally defined as the period from the initiation of any study procedures to the end of the study treatment follow-up. The start of study procedures is considered to be the point of consent. Any AEs which fit the protocol defined reportable events must be reported from the time of consent until study completion.

At each contact with the subject the investigator must seek information on AEs by specific questioning and, as appropriate, by examination. Information on protocol defined AEs should be recorded immediately in the source document and also in the appropriate AE module of the CRF. All clearly related signs, symptoms and abnormal diagnostic procedure results should be recorded in the source document and grouped under one diagnosis as appropriate. The clinical course of each event should be followed until resolution or until it is determined at the end of the study that the AE will not resolve.

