## 2.2 Safety

All operative site events as well as all serious adverse events (SAEs), excluding elective procedures, will be collected and reviewed against published data. It is expected that the AE rates reported for the Triathlon TS Total Knee System will be comparable to those reported in

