## 9.2.2 Safety Analysis

All AEs will be listed, tabulated and summarized by event, number and percent of cases/subjects. AE rates and 95% confidence intervals will be presented. In addition, a Fisher's exact test will be used to compare the AE rates between the subgroups or cohorts, if appropriate.

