#### CONFIDENTIAL

In the event a subject does not have surgery, Stryker should be contacted to discuss if/when the surgery will be rescheduled. If the surgery is rescheduled more than 4 months from the date of preoperative data collection, the subject will need to be re-consented, all preoperative data will need to be re-collected and all original preoperative data will need to be removed from the database. If the surgery is not to be rescheduled or if the subject is no longer considered an appropriate study candidate, a Study Termination CRF may be completed only after notifying Stryker of the subject's status and being given approval to terminate.

When a subject completes the study according to protocol, including the final study evaluation, a Study Termination CRF will be completed.

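### AE rates presented for the Triathlon TS system have no onset condition, so new events between consent and implantation count in them

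*Combined protocol and SAP*

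**What the plan says.** **When reporting starts.** Under Adverse Event Reporting Period in Section 8.1, "The start of study procedures is considered to be the point of consent", and reportable events "must be reported from the time of consent until study completion". Section 7.1 states: "Consent must be obtained within four months of surgery". If surgery is postponed, Section 10.3 limits the gap: "If the surgery is rescheduled more than 4 months from the date of preoperative data collection, the subject will need to be re-consented".

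**What is reportable.** Section 8.1 names two classes: "All AEs that meet the definition of serious, excluding elective procedures" and "All AEs related to the operative site, regardless of seriousness". Section 8.2 does not require an AE to be related to the study device, but it does require a change in the subject's medical baseline. Section 8.1 (General Physical Examination Findings) sends abnormalities present at screening to the Demographics CRF as preexisting conditions. New findings after consent that meet the definition are recorded as AEs.

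**What is analyzed.** Section 9.2.1 takes every reported AE as a safety parameter. Section 9.2.2 says: "All AEs will be listed, tabulated and summarized by event, number and percent of cases/subjects". It adds AE rates with 95% confidence intervals and, where appropriate, Fisher's exact tests between subgroups or cohorts. The safety population in Section 9.4.4.2 consists of subjects who received the study system, less censored cases.

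**What the rates are for.** Section 2.2: "It is expected that the AE rates reported for the Triathlon TS Total Knee System will be comparable" to those in the literature for similar revision systems. Section 12.3 repeats that the system's complication rates will be compared with published rates.

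**The concern.** Until surgery, the operative site is the knee that carries the failed implant, or a knee between stages of a septic revision. A patient may fall and fracture bone around the old component while waiting. That is a new event that changes the baseline, and it is reportable. If the patient is then implanted, the event sits in the numerator of a rate that carries the study system's name, although the system was not yet in the body.

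At stake is the safety objective: an AE rate reported for this system and judged against published revision rates. How far the numerator is inflated depends on waiting time and on events in the waiting period, neither of which says anything about the implant. The same events would also enter any Fisher's exact test between joint-line groups. Joint-line position is set at surgery, so earlier events cannot result from it. They would add only noise or chance imbalance.

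**Working it through.** The documents state no AE rate, so there is no safety figure to reproduce. The check traces the text and then shows a range under stated assumptions.

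**Step 1: does any rule remove pre-implantation events?**
- Reporting period (8.1): opens at consent, so it does not.
- AE definition (8.2): relation to the device is not required, so it does not.
- Preexisting-condition rule (8.1): removes what was present at screening, but not what is new afterwards.
- Elective-procedure exclusion (8.1, 8.2): removes elective procedures only.
- Safety population (9.4.4.2): removes subjects who were never implanted. It selects subjects, not event dates.
- Safety parameters and analysis (9.2.1, 9.2.2): all reported AEs, with no filter on onset or relatedness.

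No section defines a treatment-emergent event or splits the tables at surgery. Followed as written, the plan counts these events.

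**Step 2: how much of the reporting window lies before implantation?** With the longest gap of 4 months and follow-up of f months, the share is 4/(4 + f):
- 1 year: 4/(4 + 12) = 25%
- 2 years: 4/(4 + 24) = 14.3%
- 5 years: 4/(4 + 60) = 6.3%

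These are upper limits on time, because four months is a maximum. They are not shares of events.

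**Step 3: effect on the any-event rate.** Let p be the true share of implanted cases with an event at or after implantation, and q the share with a reportable event between consent and surgery. Both are assumptions; neither stands in the documents. If the two are independent, the tabulated rate is 1 − (1 − p)(1 − q).

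| q | p = 10% | p = 20% |
|---|---|---|
| 1% | 1 − 0.90 × 0.99 = 10.9% | 1 − 0.80 × 0.99 = 20.8% |
| 2% | 1 − 0.90 × 0.98 = 11.8% | 1 − 0.80 × 0.98 = 21.6% |
| 5% | 1 − 0.90 × 0.95 = 14.5% | 1 − 0.80 × 0.95 = 24.0% |
| 10% | 1 − 0.90 × 0.90 = 19.0% | 1 − 0.80 × 0.90 = 28.0% |

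The increase is q(1 − p): 0.9 to 9.0 percentage points at p = 10%, and 0.8 to 8.0 at p = 20%.

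**Step 4: against sampling error.** Take the 181 cases planned in Section 9.4.2, before any censoring. At p = 20%, 181 × 0.20 = 36.2, so 36 cases: 19.9%, exact 95% CI 14.3 to 26.5. At q = 5%, 181 × 0.24 = 43.4, so 43 cases: 43/181 = 23.8%, exact 95% CI 17.8 to 30.6. The shift is smaller than the half-width of either interval, but it is systematic and a larger sample would not remove it.

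**Step 5: after the fix.** If only events with onset at or after the start of implantation are counted, q drops out and the rate is p.

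**The case against.** The case against has several parts, and some of them stand.

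*The protocol already limits what counts before surgery.* This stands in part. Symptoms and findings of the failed knee that were present at screening are not AEs, and a later event must change the baseline. A reader might infer that the ordinary course of the failed implant is charged to the study system; the documents do not support that. Nor do they support treating two particular events as clear cases. A hospital stay for a planned first-stage removal may fall under the elective-procedure exclusion, whose list of examples is expressly open. Worsening of instability already recorded at screening may not qualify as new. An infection must be cleared before implantation, and a patient who is never implanted leaves the safety population. Long delays require new consent and new preoperative data, although Section 10.3 does not say what happens to AEs already reported. A new fracture around the old implant meets none of these limits.

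*An AE rate is not a count of device-caused events.* This stands. Section 8.2 includes unrelated events by definition and defines adverse device effects separately, and Section 8.3 asks for an assessment of association. An onset filter will not turn the AE rate into a device-caused rate. But Section 9.2.2 does not use relatedness, and an event after implantation could at least be a consequence of the procedure or the implant. One before it could not.

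*Reporting from consent is sound practice.* Agreed. The gap is in the analysis rule, not in the collection.

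*The effect is small and has little decision weight.* This stands in part. Four months is a maximum, the published comparison has no named reference rate, margin or test, and the bias works against the device, so it cannot hide a signal by lowering the any-event rate. Those facts limit the severity but do not make the numerator right.

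*Some operational text cannot be seen.* The AE decision tree and the CRFs are not in the text available for review. The AE form may separate preoperative events. Even so, Section 9.2 gives no instruction to use such a field.

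**Conclusion.** The point holds in a limited form. As written, the plan counts new reportable events between consent and implantation in the AE rates presented for the Triathlon TS system, provided the subject is later implanted. The direction is certain: the any-event rate can only rise. The size cannot be computed from the documents. Under the assumptions above (1% to 10% of implanted cases affected, independently of later events, and a true post-implant rate of 10% or 20%), the increase runs from 0.8 to 9.0 percentage points. The low end is as compatible with the documents as the high end.

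A reader might infer a fixed inflation of about 5 points, for example from 36/181 = 19.9% to 45/181 = 24.9%. That needs nine cases with an event before surgery and none in five years afterwards, and neither condition can be drawn from the documents. With 5% affected and independence, the shift at a 20% rate is 4.0 points.

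The effect is confined to AE rates, their confidence intervals, any subgroup tests on them and a descriptive comparison with the literature. The study device's revision rates, its radiographic rates and the primary KSS analysis do not depend on it. The change is still worth making before analysis, because it removes a known bias at almost no cost.

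**What to change.** Keep AE collection from consent as it is. In Section 9.2.2, add that AE rates, their 95% confidence intervals, any subgroup or cohort comparisons and the comparison with published rates are based on events with onset at or after the start of the study implantation surgery, intraoperative events included. Add that events with onset between consent and the start of surgery are listed separately and stay outside those rates. Section 9.2.1 should refer to the same rule.

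The cost is a sentence or two of text, one date filter and one extra listing. Section 8.3 already names the date of onset as an item of the initial report. The sponsor should confirm that the AE form records it for every reportable event and that, for events on the day of surgery, it shows whether onset came before or after the start of the operation. No event is lost from the safety report.
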